3.1. Primary Outcome

The primary outcome of the study will be calculated using the Columbia Muscle Cramp Scale (MCS). We will use MCS item #5, visual analog scale (VAS) (0-10) for Muscle Cramps Affecting Overall Daily Activity of Columbia MCS as the primary outcome. The MCS will be assessed on the phone twice a week; thus, there will be a total of four MCS assessments per treatment period. However, for the primary analysis, only data in the second week of each treatment period will be used to minimize carryover effects.

3.2. Statistical Analysis for the Primary Outcome

The primary analysis will be performed using linear mixed effect (LME) model to estimate the effect of TJ-68 compared to placebo on MCS VAS. The LME model will use all available MCS VAS measured in the second week of all treatment periods per mITT. The model will include TJ-68 as a main effect with a random participant effect to account for within-individual correlation. While balanced randomization of Treatment Sequences A and B will eliminate linear time trend, we will also explore linear and non-linear time effects in the LME model to explore the impact on the primary comparison between TJ-68 and Placebo.

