2.3. Analysis Populations and Missing Data

All efficacy analyses will be performed using the modified intent-to-treat (mITT) population. The mITT population consists of all randomized participants with outcomes evaluated in at least two (out of four) post-randomization periods with at least one period in TJ-68 and one in Placebo.

As sensitivity analyses, we will also perform efficacy analyses in the completers only, that is, participants with outcome evaluated in all 4 treatment periods.

Safety analyses will be performed as treated.

Missing data patterns will be compared by treatment sequence as well as by the treatment periods. While the primary analyses will be performed in the mITT population defined above, we will perform sensitivity analyses using imputed data sets under different imputation approaches:

- (A) Mean imputations: Missing data within a treatment period will be imputed using averages from other data points within the same treatment period. If data in the entire treatment period is missing, the observations from the previous period will be carried forward.
- (B) Worst-outcome imputations: All missing data will be imputed using the worst values observed in a treatment group.

3. Primary Efficacy Analysis

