3.3. Sample Size Consideration

We aim to enroll 22 evaluable participants equally to the two alternating TJ-68/Placebo sequences over the four treatment periods, i.e., each participant will have 4 observations. Under the LME model, assuming a within-participant standard deviation of 1.4 based on our pilot data, this sample size will yield about 85% power to detect a 1-point shift on MCS VAS. Assuming 15% attrition, we will plan to enroll a total of 22 participants.

4. Safety Analysis

Adverse events (AE), including the presence of hypokalemia, will be summarized by treatment per participant. The AE will be attributed to the period in which it is observed. AE rate by treatment will be summarized using proportion and 95% confidence intervals and will be compared using McNemar test. Longitudinal AE data will be modeled using generalized linear mixed effect model with a logit link.

5. Secondary Outcome Analyses

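### The unit of the primary analysis is not settled: sections 3.1 and 3.2 read literally give up to 8 rows per participant, section 3.3 gives 4, and the 8-row model understates the standard error if same-period ratings correlate beyond the participant effect

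*Combined protocol and SAP*

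**What the plan says.** Under section 2.1 each participant has four two-week periods, two on each treatment, in one of two mirrored sequences. Treatment is therefore constant within a period.

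On the outcome, section 3.1 says: "The MCS will be assessed on the phone twice a week; thus, there will be a total of four MCS assessments per treatment period". For the primary analysis, "only data in the second week of each treatment period will be used to minimize carryover effects". That leaves two usable ratings per period.

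On the model, section 3.2 says: "The LME model will use all available MCS VAS measured in the second week of all treatment periods per mITT". It adds: "The model will include TJ-68 as a main effect with a random participant effect to account for within-individual correlation". No section averages the two ratings or selects one of them, and none adds a participant-by-period effect or a residual correlation structure.

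Section 3.3, describing power under the LME model, says that "each participant will have 4 observations". Section 2.3 also thinks in periods: the mITT set requires "outcomes evaluated in at least two (out of four) post-randomization periods", and the completers are "participants with outcome evaluated in all 4 treatment periods". Yet the imputation rule 2.3(A) fills a gap from the other values of the same period, so there a period holds several data points. Section 5.1 analyses the secondary MCS endpoints in the same way as the primary outcome.

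**The concern.** Two analysts could follow this SAP faithfully and fit different models to the primary outcome, one with up to 8 rows per participant and one with 4. The difference matters because the period, not the rating, is the unit to which treatment is assigned. A participant intercept absorbs only the correlation that all of a participant's ratings share. Two ratings from the same week may also share short-term cramp status that ratings from other periods do not. If so, the 8-row model counts the second rating as more new information about treatment than it carries. The standard error of the TJ-68 effect, its confidence interval and its p-value would then be affected. The choice of unit could also be made after the results are seen.

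**Working it through.** **Inputs.** From the documents: 22 evaluable participants, 4 observations each, SD 1.4, a 1-point shift and about 85% power (3.3); 4 periods, 2 per treatment (2.1); 2 ratings a week, week 2 only (3.1). Assumed: a two-sided 5% test, since no alpha is stated; complete data; independent period errors; no participant-by-treatment variation. Rho is the correlation of the two same-period ratings after the participant effect is removed. The documents do not give it, so it is shown as a range.

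**The plan's own figure.** SE = 1.4 × sqrt(2/(22k)), with k rows per treatment per participant.

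- 4 rows (k = 2): SE = 1.4/sqrt(22) = 0.298. Power = Φ(1/0.298 − 1.96) = 0.918, or 0.910 and 0.891 by noncentral t with 65 and 21 df.
- 8 rows taken as independent (k = 4): SE = 1.4 × sqrt(2/88) = 0.211. Power = 0.997.

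Neither gives 85% at N = 22, but 4 rows come closer. With 4 rows and 18 evaluable participants (22 × 0.85 = 18.7, rounded down), power is 0.858. This comparison is only suggestive, because 3.3 does not say whether 1.4 refers to one rating or to a period value.

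**True variance of the effect.** Let V be the within-participant variance of one rating. A period mean of two ratings has variance V(1+rho)/2. Each participant contributes two periods per treatment, so

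Var(effect) = V(1+rho)/(2N), with N = 22.

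**What the 8-row model uses.** It has 22 × 7 − 1 = 153 residual df. Of these, 22 × 4 = 88 lie within periods, with expected mean square V(1−rho). The other 22 × 3 − 1 = 65 lie between periods, with expected mean square V(1+rho). The model pools them:

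E(MS) = V[88(1−rho) + 65(1+rho)]/153, and model variance = E(MS)/(2N).

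The factor by which the true SE exceeds the model SE is sqrt{(1+rho)/(E(MS)/V)}. At rho 0.3, E(MS)/V = (61.6 + 84.5)/153 = 0.955, so the factor is sqrt(1.3/0.955) = 1.17. Approximate type I error is 2Φ(−1.96/factor). V cancels, so the result does not depend on the SD of 1.4.

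| rho | E(MS)/V | True SE / 8-row SE | Type I, formula | Type I, simulated | Readings disagree on significance, null trials | Interval width, period means / 8 rows |
|---|---|---|---|---|---|---|
| 0 | 1.000 | 1.00 | 5.0% | 5.2% | 1.2% | 1.01 |
| 0.1 | 0.985 | 1.06 | 6.4% | 6.3% | 1.8% | 1.07 |
| 0.2 | 0.970 | 1.11 | 7.8% | 7.8% | 2.8% | 1.12 |
| 0.3 | 0.955 | 1.17 | 9.3% | 9.3% | 4.3% | 1.18 |
| 0.5 | 0.925 | 1.27 | 12.4% | 12.2% | 7.2% | 1.29 |

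Simulated values rest on 40,000 null trials per rho (Monte Carlo SE 0.1 to 0.2 percentage points). Four period means gave 4.9% to 5.2% under the same assumptions. With complete data the two analyses give the same treatment estimate.

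**The case against.** The strongest reply is that one value per period is what the SAP intends. Section 3.3 counts four observations and ties them to the LME model, 2.3 defines its analysis sets by period, 3.1 speaks of an outcome that is calculated, and the stated power is nearer to 4 rows. This has weight, and on that reading the problem does not arise. It does not settle the matter. Section 3.2 calls for every available week-2 rating, 2.3(A) treats a period as holding several values, the 85% is not reproduced exactly by either count at N = 22, and 3.3 may be a planning simplification.

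A second reply is that the random participant effect already handles correlation. That is right for correlation shared equally across all of a participant's ratings: it corresponds to rho = 0, where the 8-row standard error is correct. A reader might infer that any correlation between the two ratings is harmful. It is not; only the part beyond the participant effect is.

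A third reply is that the size is unknown. That also stands. The same formula reaches about 19% at rho 0.9, and a reader might take that as the expected inflation. The documents give no rho, so they do not support any particular value, and the upper end should not set the weight of this point.

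**Conclusion.** The inconsistency is real and should be fixed before analysis; confidence is moderate. The harm needs two conditions: 3.2 is followed literally, and same-period ratings are positively correlated beyond the participant effect. Under the assumptions listed above, type I error is then about 6% to 12% for rho 0.1 to 0.5. The direction holds for any rho above 0; the size is an assumed range.

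Two stronger conclusions are not supported. First, a reader might infer that the treatment estimate is biased. With complete data it is identical under both readings; only the SE, interval and p-value change. Second, a reader might infer that one value per period guarantees 5%. That needs independent period errors and no participant-by-treatment variation, and section 5.3 itself plans to explore heterogeneous effects. In illustrative simulations of the 4-row model with a zero mean effect, type I error is about 5.8%, 6.9% and 8.6% when participant-by-treatment variance is 0.1, 0.25 and 0.5 times the period-level variance. With serial correlation of 0.2, 0.4 and 0.6 across periods it is about 4.7%, 4.1% and 3.2%.

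**What to change.** State in section 3.2 that the response is the mean of the available week-2 MCS VAS ratings in each period, one value per participant-period. This matches the 4 observations in 3.3. Section 3.3 should also say whether the SD of 1.4 refers to one rating or to a period value.

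An acceptable alternative is to keep both ratings, add a random participant-by-period effect, and align 3.3. Its simulated type I error was 4.6% to 5.2%. When the period variance is estimated as zero it collapses to the 8-row model, with probability P(F(65,88) ≤ (1−rho)/(1+rho)): about 50%, 20%, 4% and 0.5% at rho 0, 0.1, 0.2 and 0.3. The options also differ when a rating is missing: the plain mean gives a one-rating period full weight, whereas the mixed model weights it differently. The SAP should therefore name one as primary, and apply it to the 5.1 endpoints that are rated more than once in a period.

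The cost is one or two sentences and a line of model code. The downside is a wider interval when rho is above 0, on average about 1.07 to 1.29 times the 8-row width at rho 0.1 to 0.5, which is the width the data would then support.

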3.3. Sample Size Consideration

We aim to enroll 22 evaluable participants equally to the two alternating TJ-68/Placebo sequences over the four treatment periods, i.e., each participant will have 4 observations. Under the LME model, assuming a within-participant standard deviation of 1.4 based on our pilot data, this sample size will yield about 85% power to detect a 1-point shift on MCS VAS. Assuming 15% attrition, we will plan to enroll a total of 22 participants.

4. Safety Analysis

Adverse events (AE), including the presence of hypokalemia, will be summarized by treatment per participant. The AE will be attributed to the period in which it is observed. AE rate by treatment will be summarized using proportion and 95% confidence intervals and will be compared using McNemar test. Longitudinal AE data will be modeled using generalized linear mixed effect model with a logit link.

5. Secondary Outcome Analyses

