2.1. Design Overview

This is a multi-period crossover study where each participant will receive four 2-week treatment periods of TJ-68/placebo. We plan to randomize a total of 26 participants, with 13 randomized to Treatment Sequence A: TJ-68-Placebo-Placebo-TJ-68, and another 13 to Treatment Sequence B: Placebo-TJ-68-TJ-68-Placebo, with a 1-week washout period between treatment periods. That is, each participant will receive TJ-68 and Placebo each in two separate treatment periods. Assuming 15% attrition, we expect to have 22 evaluable participants. Balanced randomization of the two alternating treatment sequences will eliminate linear trend in the primary analysis.

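### Section 3.3 attaches 85% power to 22 evaluable participants, a sample that gives about 91% at two-sided 5%; 85% fits 18 to 19, because 22 serves as both the evaluable and the enrolled number and no alpha is stated

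*Combined protocol and SAP*

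**What the plan says.** The inputs to the power statement are all in section 3.3, apart from the significance level.

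- Sample: "We aim to enroll 22 evaluable participants equally to the two alternating TJ-68/Placebo sequences over the four treatment periods", with the gloss that "each participant will have 4 observations".
- Variability: "assuming a within-participant standard deviation of 1.4 based on our pilot data".
- Result: "this sample size will yield about 85% power to detect a 1-point shift on MCS VAS".
- Enrolment, in the closing sentence of the same paragraph: "Assuming 15% attrition, we will plan to enroll a total of 22 participants".

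Section 2.1 confirms the allocation within a participant ("each participant will receive TJ-68 and Placebo each in two separate treatment periods") but gives a different total: "We plan to randomize a total of 26 participants", of whom 22 are expected to be evaluable after 15% attrition. Section 2.2 agrees with 2.1: 22, plus up to two more per sequence for dropout, is 26.

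Section 3.2 specifies a linear mixed model with a treatment effect and a random participant effect. Neither 3.2 nor 3.3 gives an alpha or says whether the primary test is one- or two-sided.

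**The concern.** In 3.3 the power is a property of a named sample, 22 evaluable participants with complete data. A reader who puts the stated inputs into the standard formula at the usual two-sided 5% does not get 85%. The same paragraph then gives 22 as the number to enrol after allowing for 15% attrition, which cannot also leave 22 evaluable.

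At stake is how a null result will be read. From the text as it stands, one cannot tell whether attrition has already been taken out of the 85%, whether a stricter test is planned, or how many participants the trial can lose before power falls below the stated level.

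**Working it through.** **Inputs.** Difference 1 point, within-participant SD 1.4, four observations per participant (3.3); two periods on each treatment (2.1); mixed model with a random participant effect (3.2). Alpha is not given, so two-sided 5% is assumed unless noted.

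**Formula.** In this balanced design participant effects cancel from the treatment contrast. With n participants there are 2n observations per treatment, so

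SE = 1.4 × √(1/(2n) + 1/(2n)) = 1.4/√n.

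The noncentrality is 1/SE. Error df are 4n − n − 1 = 3n − 1; a more conservative choice is n − 1.

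**Step 1: where 85% comes from.** Solving for n with the normal approximation, n = (1.96 + 1.036)² × 1.4² = 17.6, so 18 participants. Allowing for 15% attrition, 18/0.85 = 21.2, so 22 enrolled. That is exactly the enrolment total in the last sentence of 3.3. Going forwards, 22 × 0.85 = 18.7 remain:

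| n analysed | SE | t, 3n − 1 df | Normal | Simulated (40,000 trials) |
|---|---|---|---|---|
| 18 | 0.330 | 84.5% | 85.8% | 84.4% |
| 19 | 0.321 | 86.4% | 87.6% | 86.3% |

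So 85% is reproduced at two-sided 5% with 18 to 19 participants. With the conservative n − 1 df the same sizes give 81.5% and 83.7%, a looser match.

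**Step 2: the sample that 3.3 attaches it to.** For n = 22, SE = 1.4/√22 = 0.2985 and noncentrality = 3.35.

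| Method | Power |
|---|---|
| t, 65 df | 91.0% |
| Normal | 91.8% |
| t, 21 df | 89.1% |
| Simulated (40,000 trials) | 91.1% |

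The 65 df figure is 6 points above the stated value, and even the conservative one is 4 points above. At 85% power, the difference that 22 complete participants can detect is 0.91 points (t, 65 df).

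**Step 3: the enrolment figures.** Section 2.1: 26 × 0.85 = 22.1, so 22 evaluable. Section 2.2: 22 + 2 × 2 = 26. Section 3.3: 22 enrolled, so 18.7 evaluable. The first two agree; the third does not.

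**Step 4: the missing alpha.** With 22 participants and four observations each:

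| Test | Power |
|---|---|
| Two-sided 5% | 91.0% (t) |
| Two-sided 2.5% | 85.2% (t), 86.6% (normal) |
| One-sided 5% | 95.6% (normal) |
| One-sided 1% | 84.7% (normal) |
| Two-sided 1% | 78.1% (normal) |

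A stricter alpha would therefore also yield about 85% at 22, and nothing in the text rules it out.

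**The case against.** The best defence is that 85% does follow from section 3.3. Its last sentence supplies 15% attrition and 22 enrolled, and Step 1 shows that 85%, 15% and 22 then fit together at two-sided 5%. This stands, and it is probably how the figure arose. A reader might infer from Step 2 alone that the plan's main planning figure is simply wrong; the document does not support that, since it contains a route to 85%. But the route is inferred. It requires setting aside the word evaluable in the first sentence of 3.3, it conflicts with the 26 in 2.1 and 2.2, and no section names 18 or 19 as the evaluable number. It moves the fault from the power figure to the label on 22, and 3.3 needs correcting either way.

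A second defence is that alpha is unstated, so 91% rests on the reviewer's assumption. That also stands, and is why 91% should not be written in unconditionally.

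A reader might also infer that the trial is underpowered because section 2.3 admits participants with "outcomes evaluated in at least two (out of four) post-randomization periods", whereas 3.3 counts four observations each. Section 2.3 defines the mITT population without equating it with the evaluable number in 3.3, and nothing suggests that participants in general will supply only two periods.

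**Conclusion.** The point holds as an internal inconsistency. At two-sided 5%, the sample named in 3.3 has about 91% power (89% on conservative df), while the stated 85% belongs to about 18 to 19 participants. One number, 22, is doing duty as both the evaluable and the enrolled count, against 26 randomized in 2.1 and 2.2, and without an alpha the reader cannot settle which was meant.

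The direction is conservative. If 22 are evaluable, as section 2 plans, power at two-sided 5% is higher than stated; if 22 are enrolled, it is about 85%. Neither shows an underpowered trial.

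The figures assume complete four-period data and one value per period with SD 1.4. Section 3.1 schedules two calls in the second week, and 3.2 uses all second-week values, so the model may receive up to eight values per participant. Whether 1.4 describes a single call or a period mean is not stated. If it describes a single call, power would be higher still, up to an upper bound of 99.7% were all eight values independent given the participant effect.

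**What to change.** Change the wording of section 3.3 as follows.

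1. State the alpha and sidedness of the primary test. If something stricter than two-sided 5% was intended, say so here and apply the same level to the test in 3.2.
2. Correct the closing enrolment sentence to agree with the 26 randomized in 2.1 and 2.2, so that 22 means evaluable throughout.
3. Restate power for the number actually meant. If the test is two-sided 5%: about 91% with 22 evaluable participants observed in all four periods (detectable difference about 0.91 points at 85% power), and about 85% with 18 to 19. The 91% should go in only once the sponsor has confirmed the alpha and that 22 is the evaluable number.

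The cost is a few sentences in the SAP. The section 2 randomization target, trial conduct and the analysis model are unchanged.

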2.2. Randomization Procedures

The 22 evaluable participants will be randomized 1:1 to the two treatment sequences based on the study schedule, using blocked randomization stratified by site. To ensure power with anticipated dropout (15%), we anticipate randomizing up to 2 additional participants to each treatment sequence.

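### Section 3.3 gives 22 both as the evaluable number and as the total to enroll after allowing for 15% attrition; the total should read 26, as in section 2.1

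*Combined protocol and SAP*

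**What the plan says.** Three sections of the SAP deal with the number of participants.

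- Section 3.3 (Sample Size Consideration) opens with "We aim to enroll 22 evaluable participants equally to the two alternating TJ-68/Placebo sequences". It then gives the power claim, "this sample size will yield about 85% power to detect a 1-point shift on MCS VAS", and ends with "Assuming 15% attrition, we will plan to enroll a total of 22 participants".
- Section 2.1 (Design Overview) says "We plan to randomize a total of 26 participants", 13 to each sequence, and adds "Assuming 15% attrition, we expect to have 22 evaluable participants".
- Section 2.2 (Randomization Procedures) says "The 22 evaluable participants will be randomized 1:1 to the two treatment sequences" and, to cover the same 15% dropout, "we anticipate randomizing up to 2 additional participants to each treatment sequence".

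Section 3.3 bases its power on an SD of 1.4 within a participant, taken from pilot data, and on 4 observations per participant. It gives neither a significance level nor whether the test is one- or two-sided. Sections 3.1 and 3.2 describe two telephone assessments a week and a primary model that uses every available VAS value from the second week of each period.

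**The concern.** Section 3.3 uses one number for two different quantities. If 22 is what remains after attrition, it is not the total to enroll. If it is the total to enroll, the plan's own attrition rate leaves fewer than 22 evaluable. The sentence invokes attrition in order to arrive at a total, so it cannot be read as merely repeating the evaluable target.

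Section 3.3 is the sample size justification, and it is where a reader will look for the planned total. A reader who took 22 from it would have a figure 4 below the one in section 2.1. On the plan's 15% assumption, that reader would also miss the target of 22 evaluable on which sections 2.1, 2.2 and 3.3 all rest.

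**Working it through.** **Enrollment.** Inputs: 22 evaluable (2.1, 2.2, 3.3); 15% attrition (2.1, 2.2, 3.3); 26 randomized (2.1); up to 2 extra per sequence (2.2).

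1. Section 2.1 reproduces. Required total = evaluable/(1 − attrition) = 22/0.85 = 25.9, rounded up to 26. In the other direction, 26 × 0.85 = 22.1. The cruder rule of adding 15% gives 22 × 1.15 = 25.3, which also rounds up to 26.
2. Section 2.2 is consistent with it: 22 + 2 × 2 = 26 at most.
3. The closing sentence of 3.3 does not reproduce. A total of 22 leaves 22 × 0.85 = 18.7 evaluable, which is 3.3 below target. The stated total is 26 − 22 = 4 too low, or 4/26 = 15%.

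Nothing in these steps needs a figure from outside the documents.

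**Power (conditional note).** Inputs from 3.3: SD 1.4, shift of 1 point, 4 observations per participant. With one value per period, that is two on each treatment (2.1). Alpha is not given; two-sided 5% is my assumption.

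1. Under the random-participant model in 3.2, a participant's own level cancels from the difference between treatment means. The variance of that difference for one participant is 1.4² × (1/2 + 1/2) = 1.96, so SE = 1.4/√n.
2. At n = 22, SE = 1.4/√22 = 0.2985, and shift/SE = 1/0.2985 = 3.35.
3. Power at two-sided 5%:

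| Method | Power, 22 evaluable |
|---|---|
| Normal | 91.8% |
| t, 3n − 1 = 65 df | 91.0% |
| t, n − 1 = 21 df | 89.1% |

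The stated figure of about 85% is therefore not reproduced under this assumption; the result is 4 to 7 points higher. A one-sided 5% test moves further away (94.5–95.6%).

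4. Sections 3.1 and 3.2 allow two second-week values per period, hence up to 8 per participant. If 1.4 were the SD of a single call and errors were independent, SE = 1.4/√44 = 0.211, shift/SE = 4.74, and power is about 99.7% (normal, two-sided 5%). Independence of two calls in the same week is optimistic, so this is an upper bound.

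**The case against.** The strongest reply is that the operative number is already in the SAP. Section 2.1 gives 26, 13 per sequence, the attrition rate and the 22 evaluable, and section 2.2 is compatible with it. One figure in one sentence is out of line, and section 2.2, which governs randomization, does not repeat it. This stands, and it makes the point a minor correction. It does not make the sentence right.

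It could also be said that section 2.2 blurs the two numbers, because it speaks of randomizing evaluable participants. Under section 2.3 "The mITT population consists of all randomized participants with outcomes evaluated in at least two (out of four) post-randomization periods", with at least one on each treatment, so membership cannot be known at randomization. The wording is loose, but its next sentence adds the dropout allowance and leads to a ceiling of 26. It does not conflict with 2.1.

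Two stronger readings are tempting, and the documents do not support either.

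- A reader might infer that the 85% really describes 22 enrolled less 15%, because 18.7 evaluable at two-sided 5% gives about 83–87%. The match is back-solved. No section mentions 18, 19 or 20 participants, and the power sentence in 3.3 follows directly from the 22 evaluable and refers to them.
- A reader might infer that enrolling 22 would leave the trial short of power, at about 73–80%. That result needs a two-sided 2.5% level, which the documents nowhere suggest; its only attraction is that it returns about 85% at 22 evaluable. At two-sided 5%, 18.7 evaluable gives roughly the power claimed. Both calculations also treat every dropout as wholly lost, whereas the mITT rule keeps some of them.

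**Conclusion.** The closing sentence of section 3.3 is wrong as written. With 22 evaluable and 15% attrition the total is 26, not 22. The error is 4 participants and rests only on the plan's own figures. Section 2.1 already gives the correct number, so this is a minor correction of a stated sample size. It does not threaten the design or the validity of the trial, and no material loss of power has been shown.

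The power note is conditional. The 85% belongs to 22 evaluable participants, but it cannot be verified without an alpha. At an assumed two-sided 5% with 4 observations each, power is about 89–92%, and it rises if both second-week calls enter as separate observations. On that assumption the stated figure errs on the cautious side. This is an omission in reporting and not a proven error in the power.

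**What to change.** Replace the last sentence of section 3.3 with: *Assuming 15% attrition, 26 participants (13 per sequence) will be randomized to obtain 22 evaluable.*

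In the same edit, state the alpha, its sidedness and the number of observations per participant behind the 85%, including whether the two second-week calls count as one value per period or two. If those inputs do not give 85% at 22 evaluable, restate the power to match.

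The cost is SAP wording only. It needs no participants beyond the 26 in section 2.1, and no change to the design or the analysis.

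### If excess AE risk on TJ-68 outlasts the 1-week washout, the section 4 attribution rule counts it as placebo, and no planned analysis would show it

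*Combined protocol and SAP*

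**What the plan says.** Section 2.1 of the SAP sets the structure: "each participant will receive four 2-week treatment periods of TJ-68/placebo", "with a 1-week washout period between treatment periods". The two sequences are "Treatment Sequence A: TJ-68-Placebo-Placebo-TJ-68" and "Treatment Sequence B: Placebo-TJ-68-TJ-68-Placebo".

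Section 3.1 has two telephone assessments a week, but for the primary efficacy analysis "only data in the second week of each treatment period will be used to minimize carryover effects". Week 1 is set aside even though a washout precedes every period after the first.

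Section 4 treats safety differently. "The AE will be attributed to the period in which it is observed", and "AE rate by treatment will be summarized using proportion and 95% confidence intervals and will be compared using McNemar test". Hypokalemia falls under the same rule. A logit mixed model for longitudinal AE data is also planned, but its time unit and covariates are not given. Section 2.3 adds only that "Safety analyses will be performed as treated". Neither section gives a lag window, a carryover term or a sensitivity analysis for AEs.

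**The concern.** The plan guards against one risk for efficacy and leaves it unguarded for safety. Week 1 of a period counts in full toward that period's treatment when AEs are assigned. A late TJ-68 effect that first appears in week 1 of the following placebo period therefore becomes a placebo AE.

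For any harm that TJ-68 increases, the error runs one way: it raises the placebo rate and makes TJ-68 look safer. In the paired comparison, a participant with an AE on TJ-68 and a late one on placebo becomes a tie. A participant whose only AE is the late one becomes a discordant pair in placebo's disfavour. The proportions and the mixed model are affected in the same direction. Safety is a stated aim of the trial (section 1).

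Attributing AEs by onset date would not help, because these AEs begin inside the placebo period.

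**Working it through.** The SAP states no AE figure, so there is none to reproduce.

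**Exposure count (sequences from 2.1).** In A (T-P-P-T) the placebo period following TJ-68 is period 2; in B (P-T-T-P) it is period 4. Each completer has two 2-week placebo periods, or 4 placebo weeks, and exactly 1 of them is week 1 of a placebo period following TJ-68. With the 1-week washout, that week covers days 8 to 14 after the TJ-68 period ends.

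**Weekly rate scale.** Let h0 and h1 be the weekly AE risks on placebo and TJ-68, and let f be the share of the excess h1 − h0 that persists in that one week.

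- Average placebo risk = [3·h0 + h0 + f(h1 − h0)]/4 = h0 + f(h1 − h0)/4
- Observed difference = (h1 − h0)(1 − f/4)

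The shrinkage is f/4 whatever the risks: 0% at f = 0, 6.25% at f = 0.25, 12.5% at f = 0.5 and 25% at f = 1.

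**Ever/never scale, as McNemar uses it.** TJ-68 proportion = 1 − (1 − h1)^4. Placebo proportion = 1 − (1 − h0)^3·(1 − h0 − f(h1 − h0)). The weekly risks are assumptions. Power is for an exact two-sided 5% McNemar test with n = 22 (the evaluable number in 2.1 and 3.3), assuming independence within participant.

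| h0, h1 | TJ-68 | f | Placebo | Difference (points) | Shrinkage | Power |
|---|---|---|---|---|---|---|
| 5%, 15% | 47.8% | 0 | 18.5% | 29.2 | 0% | 40.1% |
| | | 0.25 | 20.7% | 27.1 | 7.3% | 33.7% |
| | | 0.5 | 22.8% | 25.0 | 14.7% | 28.0% |
| | | 1 | 27.1% | 20.7 | 29.3% | 18.5% |
| 3%, 10% | 34.4% | 0 | 11.5% | 22.9 | 0% | 28.7% |
| | | 0.5 | 14.7% | 19.7 | 13.9% | 19.9% |
| | | 1 | 17.9% | 16.5 | 27.9% | 13.5% |

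For example, 1 − 0.85^4 = 0.478 and 1 − 0.95^4 = 0.185; at f = 0.5 the placebo figure is 1 − 0.95^3 × 0.90 = 0.228.

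**Period balance of possible remedies.** TJ-68 occupies periods 1 and 4 in A and 2 and 3 in B: mean (1+4+2+3)/4 = 2.5. All placebo periods together also average (2+3+1+4)/4 = 2.5. The placebo periods that do not follow TJ-68 are period 3 in A and period 1 in B: mean 2.0. The ones that do are 2 and 4: mean 3.0. Setting apart the latter without a period term therefore loses the protection against linear trend that 2.1 relies on.

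Restricting to periods 1 and 3 keeps it. A contributes TJ-68 then placebo, B placebo then TJ-68, and both treatments average period 2.0 with 2 weeks each. Period 3 placebo in A starts 1 + 2 + 1 = 4 weeks after the TJ-68 period ends.

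**The case against.** A reader might infer that 3.1 concedes carryover in week 1, so that the safety comparison is biased as it stands. The documents do not support that. Section 3.1 describes a precaution for a 0-10 cramp scale, and it also drops week 1 of period 1, which no study treatment precedes. Nothing says that AE risk outlasts the washout. If none does, or if TJ-68 does not raise AE risk, this bias is zero. A reader might also picture placebo starting the day TJ-68 stops, but a full week lies between. This objection stands and makes the point conditional.

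The effect is also small beside the noise. With assumed risks of 5% and 15%, independence and n = 22, the discordant probabilities are 0.478 × 0.815 = 0.390 and 0.185 × 0.522 = 0.097. The standard error of the paired difference is √[(0.486 − 0.292²)/22] ≈ 0.135, so the 95% half-width is about 26 points. The bias is about 2 points at f = 0.25 and 9 at f = 1. That is a good reason to keep the extra analysis supportive. It is not a reason to omit it, since the direction is known and the data are already planned.

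A further objection is that a persisting effect would be expected first in the washout week, for which section 4 names no treatment. That is a real gap, but a separate one: assigning washout AEs would leave AEs starting in week 1 of placebo where they are.

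Finally, attribution to the period of observation is simple and prespecified. That is fair, and the rule can stay as the main analysis.

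**Conclusion.** The point holds conditionally. The SAP protects efficacy, but not safety, against effects that last beyond the washout. Under its attribution rule, any excess TJ-68 risk persisting into week 1 of the following placebo period is counted as placebo, which understates the difference.

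The shrinkage lies between 0% and 25% on the weekly rate scale, and is up to 27.9% or 29.3% on the ever/never scale for the two pairs of risks tabulated. These figures assume completers, constant weekly risks, a TJ-68 excess, and persistence confined to that one week. The upper end needs the excess to be undiminished after the washout. The weekly risks and f are illustrations, because the documents supply neither. Whether the bias occurs cannot be settled from the plan. As written, the plan includes no analysis that would reveal it.

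**What to change.** Keep the planned attribution as the main safety analysis and add one supportive analysis to section 4:

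1. Tabulate placebo AEs, and hypokalemia separately, for the placebo period following TJ-68 (period 2 in A, 4 in B) and for the other placebo period (3 in A, 1 in B).
2. Specify the logit mixed model at period level, and in the supportive version add an indicator for placebo following TJ-68 together with a period term. The period term is needed because the unflagged placebo periods average 2.0 against 2.5 for TJ-68.
3. As the paired counterpart, repeat the McNemar test on periods 1 and 3 only. Exposure is equal, periods are balanced between treatments, and no placebo period is immediately preceded by a TJ-68 period.

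Week 1 should not be dropped from all safety data to mirror 3.1, since that would discard TJ-68 exposure as well.

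No new data are needed. The cost is precision, because about half the exposure is used. With 2 weeks per treatment and assumed risks of 5% and 15%, the difference is (1 − 0.85²) − (1 − 0.95²) = 18.0 points and McNemar power is about 18%, against 40.1% for four weeks without carryover. The indicator sets apart the whole period, not only week 1. The model has about 22 × 4 = 88 participant-periods and may be unstable if AEs are sparse. In B, the period 3 TJ-68 exposure itself follows TJ-68. The results should be labelled supportive and read beside the main comparison.
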